# 4 Study Design

# 4.1 Overall Design

This is a randomized, open-label, active-controlled, multicenter study to investigate efficacy and safety of UV1 vaccination in combination with nivolumab and ipilimumab as first-line treatment of adult patients ( $\geq$ 18 years) with histologically confirmed unresectable metastatic melanoma.

The study is planned to be conducted at 40 study sites in Europe (approximately 16 sites) and the United States (approximately 24 sites).

This study will consist of 3 phases: Screening, Induction period, and Follow-up period. The Follow-up period includes safety, response, and survival follow-up visits.

After a Screening period of up to 28 days, eligible patients will be randomized in a 1:1 ratio to receive induction therapy: UV1 vaccination in combination with nivolumab and ipilimumab in an experimental arm, or nivolumab and ipilimumab in a control arm. Randomization can occur after all Screening procedures have been completed (up to 3 days [from Day -3 until Day 1] prior to first dosing on Day 1) and eligibility has been confirmed. It is estimated that approximately 200 patients will need to be screened in order to randomize the required 154 patients.

Patients in the experimental arm will receive 8 UV1 vaccinations over 4 cycles of nivolumab and ipilimumab. UV1 vaccination will be administered alone on Days 1, 3 to 7 (2 UV1 vaccinations within Day 3 to Day 7; consecutive dosing days not allowed), and 26, and in combination with nivolumab and ipilimumab on Days 10, 31, 52, and 73.

Patients in the control arm will receive 4 cycles of nivolumab and ipilimumab on Days 1, 22, 43, and 64.

Patients in both arms will start maintenance therapy 6 weeks after the last dose of induction therapy. The maintenance therapy is nivolumab at a dose of 480 mg every 4 weeks (Q4W) according to the label. It is not allowed to use any other dose of maintenance therapy (eg, 240 mg Q2W).

The study is event driven. The primary and secondary endpoints will be analyzed at the earliest of either 70 PFS events reached across both treatment arms or 18 months post last patient randomized, at which time the sponsor will notify the sites. From the PFS cut-off date, patients will be followed for a further 24 months for additional survival data; further analyses of OS data will be performed until defined end of study to provide evidence supportive of PFS.

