#### Figure 3 McBurney's Point

Administration of UV1 should be done **10 to 15 minutes** *after* the administration of sargramostim. The UV1 is to be administrated at the exact same site as the sargramostim.

Allergic reactions may occur after sargramostim and UV1 injections. Therefore, patients should remain at the site for observation for at least 4 hours after each UV1 injection.

Nivolumab and ipilimumab are administered intravenously according to the label and administration is to be started at least 1 hour after the injection of UV1.

Patients in the experimental arm will receive 8 UV1 vaccinations over 4 cycles of nivolumab and ipilimumab. The UV1 vaccination will be administered alone on Days 1, 3 to 7 (2 UV1 vaccinations), and 26, and in combination with nivolumab and ipilimumab on Days 10, 31, 52, and 73.

Patients in the control arm will receive 4 cycles of nivolumab and ipilimumab, on Days 1, 22, 43, and 64.

The administration of sargramostim, UV1, nivolumab, and ipilimumab must be recorded in the patients' medical files and the appropriate section of the electronic Case Report Form (eCRF). The reason for dose interruption, reduction, or omission will also be recorded in the medical files of patient and later in the eCRF. This information will be used to assess compliance with treatment.

Following the induction therapy, patients in both treatment arms will start maintenance therapy and receive nivolumab at a dose of 480 mg Q4W according to the label. It is not allowed to use any other dose of maintenance therapy (eg, 240 mg Q2W). Nivolumab is the standard of care and should be monitored according to the institutional practice (including routine blood sampling).

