# 7.2 Induction Period

Patients who satisfy all eligibility criteria will be randomized in a 1:1 ratio between the 2 treatment arms and start treatment with induction therapy:

- Experimental arm: UV1 vaccination in combination with nivolumab and ipilimumab
- Control arm: nivolumab and ipilimumab.

The combination of nivolumab and ipilimumab as induction therapy is administered Q3W for 4 doses. Patients randomized to the experimental arm will undergo 4 additional visits to receive single doses with UV1 vaccination.

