# 7.2.1 Discontinuation of Induction Therapy

If, during the Induction period, both nivolumab and ipilimumab are temporarily discontinued for patients randomized to the experimental arm, study visits and treatment with UV1 vaccination should also be temporarily discontinued. However, UV1 vaccination at visit 5 (monotherapy) can be administered if the patient would have been considered eligible to receive nivolumab and ipilimumab at that time point.

If, during the Induction period, nivolumab and ipilimumab are permanently discontinued, study visits and treatment with UV1 vaccination should be permanently discontinued. If the decision to permanently discontinue induction therapy is done during a scheduled study visit, the procedures and assessments applicable for that visit should be performed. However, if it's been > 30 days since last induction dose, the safety follow-up visit should be performed instead. If the decision to permanently discontinue induction therapy is done between two scheduled study visits, the next visit will be the safety follow-up visit which shall be performed 30-37 days after the last induction dose. If it's been > 37 days since last induction dose, the safety follow-up visit should be performed as soon as possible.

If the UV1 vaccination is discontinued, nivolumab and ipilimumab induction therapy may continue as scheduled in the protocol. With the exception of the DTH testing, all study procedures and assessments described in the schedule of activities will be performed.

Discontinuation of induction therapy does not represent withdrawal from the study. All patients that permanently discontinue all induction therapies prior to completion of the Induction period (Days 1 to 73 in the experimental arm and Days 1 to 64 in the control arm) will attend the safety follow-up visit and continue in the study for the determination of PD and survival.

UV1 vaccination will be discontinued if any of the following situations occur:

- 1. Patient requests to stop UV1 vaccination, nivolumab and ipilimumab
- 2. Any clinical AE, laboratory abnormality, intercurrent illness which, in the opinion of the Investigator, indicates that continuation with UV1 vaccination is not in the best interest of the patient
- 3. Patient starts another anticancer treatment while receiving UV1 vaccination, nivolumab, and ipilimumab
- 4. Pregnancy
- 5. At the discretion of the Investigator
- 6. Termination of the study by the Sponsor.

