## 8.3.3 Adverse Event Reporting and Follow-up

# 8.3.3.1 Reporting

Adverse events will be reported by the patient (or, when appropriate, by a caregiver, surrogate, or the patient's legally authorized representative). Care will be taken not to introduce bias when detecting AEs. Open-ended and non-leading verbal questioning of the patient is the preferred method to inquire about AE occurrence (for example, "Have you experienced any new or changed symptoms since we last asked/since your last visit?").

From signing of the ICF until the first dose of induction therapy, only AEs/SAEs caused by study-specific procedures should be reported. All non-serious AEs should be reported from the first dose of induction therapy until 30 days after the last dose of induction therapy, or until new anticancer treatment is initiated (whichever comes first).

All SAEs should be reported from the first dose of induction therapy until 70 PFS events are reached, until 18 months post last patient randomized or until new anticancer treatment is initiated (whichever comes first).

The time periods for reporting of AEs and SAEs are outlined in Figure 4.

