## 9.4.3 Safety Analyses

Adverse events will be classified using the latest version of the Medical Dictionary for Regulatory Activities (MedDRA) classification system. Treatment-emergent AEs (TEAEs) will be summarized. A TEAE is defined as an AE that was not present prior to first study treatment but appeared following treatment, or was present at treatment initiation but worsened during treatment. An AE that was present at treatment initiation but resolved and then reappeared while the patient was on treatment is a TEAE (regardless of the intensity of the AE when the treatment was initiated). For simplicity, TEAEs will be referred to as AEs in this protocol. Adverse events will be summarized descriptively by treatment arm, in terms of body system and MedDRA preferred term. Patients with multiple occurrences of the same AE will only be counted once at the maximum severity/grade for each preferred term, system organ class, and overall. Adverse events will be summarized in terms of the number and percentages of patients experiencing related AEs, SAEs, AEs leading to dose interruption, AEs leading to withdrawal from randomized treatment, and AEs leading to death. In the event that a patient experiences repeated episodes of the same AE, the patient will be counted once within each system organ class and similarly counted once within each preferred term and the event with the highest severity grade and/or strongest causal relationship to each treatment will be used for incidence tabulations.

Laboratory values and change from Baseline will be summarized using descriptive statistics at scheduled visits by treatment. Shift tables of the worst on-study laboratory toxicity relative to Baseline will be presented by treatment arm. Patient listings of Grades  $\geq$ 3 laboratory toxicities will be provided.

Vital signs and ECOG performance status (observed and change from Baseline) will be summarized using descriptive statistics by timepoint and treatment.

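### Non-serious AE percentages can be modestly inflated in the UV1 arm by a longer reporting window and more AE contacts, even if UV1 adds no harm

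*Combined protocol and SAP*

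**What the plan says.** Comparing safety between the arms is a secondary objective (Section 3). For AEs, Section 9.4.3 plans a descriptive summary by arm: "Adverse events will be summarized in terms of the number and percentages of patients experiencing related AEs, SAEs, AEs leading to dose interruption", and the list continues to withdrawals and deaths. It names no exposure-adjusted rate and no common observation period.

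Section 8.3.3.1 sets the collection window: "All non-serious AEs should be reported from the first dose of induction therapy until 30 days after the last dose of induction therapy". Collection closes sooner if another cancer therapy is started. SAEs follow a different rule in the same section. They run from the first induction dose to the PFS cut-off or new anticancer treatment.

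The schedules differ. Section 7.2.1 gives the induction period as "Days 1 to 73 in the experimental arm and Days 1 to 64 in the control arm". In Section 4.1 the UV1 arm receives UV1 "in combination with nivolumab and ipilimumab on Days 10, 31, 52, and 73", after a UV1-only lead-in from Day 1. For control: "Patients in the control arm will receive 4 cycles of nivolumab and ipilimumab on Days 1, 22, 43, and 64". Section 7.2 adds: "Patients randomized to the experimental arm will undergo 4 additional visits to receive single doses with UV1 vaccination". Tables 5 and 6 mark AE collection at every induction visit and at the safety follow-up visit. Section 6.1.5 also states, for the UV1 arm only, that "patients should remain at the site for observation for at least 4 hours after each UV1 injection".

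**The concern.** The window is tied to induction dosing, and induction begins earlier relative to nivolumab/ipilimumab in one arm. A UV1 patient is therefore observed for non-serious AEs on days that have no control counterpart. Before the first induction dose, only AEs caused by study procedures are reported (Section 8.3.3.1), so a control patient's days before nivolumab/ipilimumab contribute almost nothing. UV1 patients are also asked about AEs more often and are watched on site after each injection.

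A crude patient percentage rises with both time and detection. If the UV1 column shows more fatigue, rash or pruritus, the tables named in Section 9.4.3 do not let a reader separate added harm from added observation. Section 2.4 lists these same event types as common with UV1, so they are the ones most likely to be read across the two columns.

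**Working it through.** **Inputs.** Dosing days: Section 4.1. Induction length: Section 7.2.1. AE windows: Section 8.3.3.1. Visits and visit windows: Tables 5 and 6. The documents give no AE rate and no AE capture rate, so those are assumed below.

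**1. The plan's own figures.** Four three-weekly cycles from Day 10 end on 10 + 3 × 21 = Day 73; from Day 1 they end on 1 + 3 × 21 = Day 64. Induction visits number 8 and 4, a difference of 4. All agree with the plan.

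**2. Window at full induction.**
- UV1: 73 + 30 = Day 103, so 103 − 1 = 102 days.
- Control: 64 + 30 = Day 94, so 94 − 1 = 93 days.
- Difference 9 days; ratio 102/93 = 1.097. With ±2 days on each last visit, the nominal gap is 5 to 13 days.

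**3. Where the 9 days lie.** From the first nivolumab/ipilimumab dose, UV1 has 103 − 10 = 93 days and control has 94 − 1 = 93. The whole difference is the lead-in.

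**4. Earlier stops (window in days, UV1 against control).**

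| Last nivolumab/ipilimumab cycle | Current window | Ratio | From first to 30 days after last nivolumab/ipilimumab dose |
|---|---|---|---|
| 1 | 39 v 30 | 1.30 | 30 v 30 |
| 2 | 60 v 51 | 1.18 | 51 v 51 |
| 3 | 81 v 72 | 1.13 | 72 v 72 |
| 4 | 102 v 93 | 1.10 | 93 v 93 |

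**5. Effect of the window on a percentage at full induction, with no UV1 harm.** Let f be the AE hazard in the lead-in relative to the hazard after it, and p the control percentage. Then UV1 percentage = 1 − (1 − p)^((93 + 9f)/93).
- f = 1 (same rate throughout): 10% becomes 10.9%, 30% becomes 32.4%, 50% becomes 53.2%, 80% becomes 82.9%, 95% becomes 96.3%. The largest excess is 3.4 points, at p of about 62%.
- f = 0.5: +1.2 points at 30% and about +1.7 at 50%.
- f = 0.25: +0.6 points at 30%, +0.8 at 50%, at most about 0.9.
- f = 0: no excess.

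**6. Contacts.** After the first dose, UV1 has 8 (two in Days 3 to 7, then Days 10, 26, 31, 52, 73 and the safety visit). Control has 4 (Days 22, 43, 64 and the safety visit). After the first nivolumab/ipilimumab dose it is 5 against 4, the extra one being Day 26. Any effect on percentages is true incidence × (capture with UV1 − capture in control). Assumed capture of 95% against 90%, up to 85% against 70%, with true incidence of 30% to 70%, gives 0.30 × 0.05 = 1.5 points up to 0.70 × 0.15 = 10.5 points. The width of that range reflects the assumptions; it is not an estimate.

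**7. Exposure-adjusted rates on the current windows.** With no UV1 harm, the full-induction rate ratio is (93 + 9f)/102: 93/102 = 0.91 at f = 0 and 95.25/102 = 0.93 at f = 0.25. That would make UV1 look safer than it is.

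**The case against.** The lead-in is part of the UV1 regimen, so AEs in it belong in that regimen's safety description. This stands, and it is why the all-AE tables should stay.

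The AE question covers the whole interval since the last visit, and investigators review hospital notes and laboratory and diagnostic reports (Section 8.3.3.1). Twice the contacts need not mean much more capture. This also stands.

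The comparison is descriptive, and with 77 patients per arm the standard error of a difference at 50% is √(2 × 0.5 × 0.5/77) = 8.1 points, well above 3.4. That limits the weight of any single row. But the bias runs in one direction across all non-serious rows, and a descriptive table is still read across its columns.

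Two stronger readings are tempting. A reader might infer that a 50% control incidence would show as 54% to 62% with UV1. That follows if the chance of reporting an AE decays exponentially with time to the next visit, with a decay constant between 60 and 7 days. It also needs the full on-checkpoint AE rate during the lead-in, when no checkpoint inhibitor has been given. With lead-in hazard at zero, the same model gives 50.5% to 54%. No passage supports the decay, and at 7 days it implies that only 29% of control AEs are ever recorded.

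A reader might also note that after a cycle 1 stop, 25 of 55 UV1-arm days (45%) can lack a control counterpart. That case needs the Day 26 dose to have been given, which Section 7.2.1 allows during a temporary hold only conditionally ("UV1 vaccination at visit 5 (monotherapy) can be administered if the patient would have been considered eligible" for nivolumab and ipilimumab at that time), followed by permanent stopping before cycle 2. Without the Day 26 dose, the share is 9/39 = 23%.

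**Conclusion.** The point holds as a modest, one-directional bias in non-serious AE percentages. The unequal window and contact counts follow directly from the schedule. The 3.4-point ceiling applies to full induction and assumes a constant hazard; about 1 point or less is the more plausible size if few AEs arise before nivolumab/ipilimumab starts. Early stopping raises the window ratio for the patients concerned, but the documents give no stopping rate with which to average it. The contact effect has a direction but no size that the documents can supply.

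Three inferences go too far. The documents do not show that UV1 will look clearly more toxic. They do not extend the window argument to SAEs, although the quoted sentence includes them, because SAE collection does not end at an arm-specific induction date. And they do not show that a common-clock or exposure-adjusted summary has been ruled out: Section 9.4.1 defers detail to a SAP whose text is not in the document reviewed, so it can only be said that Section 9.4.3 plans none.

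**What to change.** Keep the current all-AE tables as the description of each regimen. Add to Section 9.4.3 and the SAP:

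- A supplementary between-arm table of non-serious AEs with onset from the first nivolumab/ipilimumab dose to 30 days after the last one. This period always lies inside the window already collected.
- A UV1-arm-only table of AEs with onset before or after that period.
- A stated denominator for the common-clock table: patients with at least one nivolumab/ipilimumab dose, with the number of UV1-arm patients who never reached it.
- If exposure-adjusted rates are given, calculation on this common clock and not on the unequal windows.

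The cost is a few extra tables from AE and dosing records already in the eCRF; no patient procedure changes. The drawback is that reactions to the lead-in injections (three of the eight) fall outside the common-clock comparison and must be read from their own table. A small detection difference remains, from 5 against 4 later contacts and the 4-hour observation after UV1.

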# 7 Study Duration and Schedule of Activities

This study will consist of 3 phases: Screening, an Induction period, and a Follow-up period. The Follow-up period includes safety, response, and survival follow-up visits.

	Screening	Induction period								Follow-up period			
Visit/Cycle		V1	V2	+ 3	V4 C1	V5	V6 C2	V7 C3	V8 C4	Safety follow- up	Response follow-up	Survival follow-up a	Survival follow- up a
Visit window		0	(	)	± 2d	± 2d	± 2d	± 2d	± 2d	+7d	±1w	±1w	+2w
Days/Weeks	D -28 to -1	D1	D3 UV1 vac Conse dosing c allo	3-7 cinations cutive lays not wed	D10	D26	D31	D52	D73	30 days post last dose of induction therapy	10w post last dose of induction therapy then every 8w for 32w. Subsequent visits every 12w until iCPD per iRECIST or PFS cut-off date reached	Every 12w from iCPD per iRECIST until PFS cut-off date reached	From time of the PFS cut-off date reached: Every 6 months for 2 years
Signed consent	Х												
Eligibility criteria	Х												
Medical history	Х												
Vital signs & ECOG	Х	Х			Х		Х	Х	Х	Х			
Physical examination	Х									Х			
Local lab analysis (all patients) b													
• Hematology & chemistry m	Х	Х			Х	Х	Х	Х	Х	Х			
Hepatitis B & C virus	Х												
Pregnancy test c	Х				Х		Х	Х	Х	Х			
Central lab sampling (all patients) d		Х					X	Х		Х	X (2 nd visit only)		
Randomization e		Х											
Treatment:			1			1			1	L	1		
UV1 vaccination		Х	Х	Х	Х	Х	Х	Х	Х				
Nivolumab					Х		Х	Х	Х	N	ivolumab 480 mg Q4W according to	label (maintenance the	erapy) f
Ipilimumab					Х		Х	Х	Х				
Adverse Events g	Х	Х	Х	Х	Х	Х	Х	Х	Х	Х	X	Х	
Concomitant medication h	Х	Х	Х	Х	Х	Х	Х	Х	Х	Х			
Subsequent anticancer treatment										Х	Х	Х	
Survival status												Х	Х
Tumor imaging i	FIRST tumor imagin SECOND tumor ima SUBSEQUENT tumo ADDITIONAL tumo	T tumor imaging during Screening at Day -14 to -1 DND tumor imaging at Week 12 and THIRD tumor imaging at Week 19 post randomization SEQUENT tumor imaging every 8 weeks for 32 weeks and then every 12 weeks until PD per iRECIST or until PFS cut-off date is reached (whichever comes first) JITIONAL tumor imaging if premature treatment discontinuation due to any cause											
Extended Explorator	y Cohort (40 patients	i) i											
Signed consent (exploratory	Х												
Fecal sample	X												
Tumor biopsy (FFPE &	Х									Х			
DNA & SNP		Х											

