#### Table 6Schedule of Activities – Control Arm

	Screening		Induction	therapy		Follow-up period				
Visit/Cycle		V1 C1	V2 C2	V3 C3	V4 C4	Safety follow-up	Response follow-up	Survival follow- up a	Survival follow- up a	
Visit window		0	± 2d	± 2d	± 2d	+7d	±1w	±1w	+2w	
Days/Weeks	D -28 to -1	Dl	D22	D43	D64	30 days post last dose of induction therapy	10w post last dose of induction therapy then every 8w for 32w. Subsequent visits every 12w until iCPD per iRECIST or PFS cut-off date reached	Every 12w from iCPD per iRECIST until PFS cut-off date reached	From time of thePFS cut-off date reached: Every 6 months for 2 years	
Signed consent	Х									
Eligibility criteria	X									
Medical history	X									
Vital signs & ECOG	X	Х	Х	Х	Х	Х				
Physical examination	Х					Х				
Local lab analysis (all patients) b			4	1						
• Hematology & chemistry  )	Х	Х	Х	Х	Х	Х				
Hepatitis B & C virus	Х									
Pregnancy test c	Х	Х	Х	Х	Х	Х				
Central lab sampling (all patients) d		Х		Х	Х	Х	X (2 nd visit only)			
Randomization e		Х								
Treatment:										
Nivolumab		Х	Х	Х	Х	Nivolumab 480 mg Q4W according to label (maintenance therapy) f				
• Ipilimumab		Х	Х	Х	Х					
Adverse Events g	Х	Х	Х	Х	Х	Х	Х	Х		
Concomitant medication h	Х	Х	Х	Х	Х	Х				
Subsequent anticancer treatment						Х	Х	Х		
Survival status								Х	X	
Tumor imaging i	FIRST tumor i SECOND tum SUBSEQUEN first)	imaging dur or imaging a T tumor ima	ing Screeni at Week 12 aging every	ng at Days and THIR 8 weeks fo	-14 to -1 D tumor in or 32 week	maging at Weeks and then ev	ek 19 post randomizatio ery 12 weeks until PD p	on per iRECIST or until the PFS cut-c	off date is reached (whichever comes	
Extended Exploratory Coho	ort (40 patients) j									
Signed consent (exploratory cohort)	Х									
Fecal sample	X									
Tumor biopsy (FFPE & snap-frozen) k	X					Х				
DNA & SNP		Х								
PBMC		Х		Х		Х	X (2 nd visit only)			

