## **Appendix 1 Clinical Laboratory Tests**

- Local laboratory analysis (all patients) are detailed in Table 7.
- Central laboratory sampling for exploratory analysis (all patients) are detailed in Table 8.
- Extended Exploratory Cohort assessments (approximately 40 patients) are detailed in Appendix 2, Table 9, and Table 10.
- Additional tests may be performed at any time during the study as determined necessary by the Investigator or required by local regulations.
- Blood samples must be collected prior to administration of treatment.

Table 7Local Laboratory Analysis (all patients, N=154)

Laboratory Assessments	Parameters		
Hematology	Red blood cell (RBC) Count Hemoglobin Hematocrit White blood cell (WBC) Count Platelet Count Absolute neutrophil count	RBC Indices: Mean corpuscular volume Mean corpuscular hemoglobin	WBC count with Differential: Neutrophils Lymphocytes Monocytes Eosinophils Basophils
Clinical Chemistry from serum or plasma 	Blood urea nitrogen (BUN)/Urea*Glucose (non-fasting) CalciumPotassiumCalciumPotassiumAlkaline phosphataseTotal and direct bilirubinAspartate aminotransferase (AST/GOT)CreatinineAlanine aminotransferase (ALT/GPT)SodiumLactate dehydrogenaseAlbuminUric acidChlorideThyroid panel (TSH and fT4)		
Other Screening Tests	
 
Hepatitis B surface antigen and hepatitis C virus antibody
 
Human chorionic gonadotropin pregnancy test (for women of childbearing potential)
 
		
NOTES:  All events of ALT or AST ≥3 × upper limit of normal (ULN) AND bilirubin ≥2 × ULN, which may indicate severe liver injury (possible Hy's Law), must be reported as a serious adverse event.  Local urine testing will be standard for the protocol unless serum or plasma testing is required by local regulation or Institutional Review Board/Independent Ethics Committee. If the urine test is positive or cannot be confirmed as negative, a serum or plasma pregnancy test will be required. *Assessment of urea to be performed by sites where laboratories are not using BUN. Total amount of blood for local analysis will be approximately 30 mL per patient.			

Investigators must document their review of each laboratory safety report.

Treatment arm	Visits	Laboratory assessments	Volume of blood
			collected

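### The worst-value laboratory shift table draws on six scheduled samples with UV1 and four in control, so with no true effect it is still expected to show modestly more toxicity with UV1.

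*Combined protocol and SAP*

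**What the plan says.** Section 3 makes the comparison of safety between arms, laboratory assessments included, a secondary objective. For the laboratory data, section 9.4.3 plans the following: "Shift tables of the worst on-study laboratory toxicity relative to Baseline will be presented by treatment arm". It does not define the on-study period, name the visits that count, or say how unscheduled results enter.

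The same section also plans descriptive summaries of values and changes from baseline at each scheduled visit, and listings of Grade 3 or higher toxicities.

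The sampling schedule is the row "Hematology & chemistry" in Tables 5 and 6:

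- **UV1 arm (Table 5):** screening, Days 1, 10, 26, 31, 52 and 73, and safety follow-up.
- **Control arm (Table 6):** screening, Days 1, 22, 43 and 64, and safety follow-up.

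Appendix 1 adds: "Blood samples must be collected prior to administration of treatment". The Day 1 sample is therefore a baseline sample in both arms.

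Section 4.1 gives the checkpoint days. UV1 is given "in combination with nivolumab and ipilimumab on Days 10, 31, 52, and 73". For control: "Patients in the control arm will receive 4 cycles of nivolumab and ipilimumab on Days 1, 22, 43, and 64".

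**The concern.** A worst-value summary depends on how often one looks. If one arm is sampled at the same four points as the other and at two more, its worst grade cannot be lower and will sometimes be higher, even if the added treatment does nothing. A by-arm table of worst grades then mixes toxicity with sampling frequency.

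This matters for three reasons.

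- Section 8.2.6 states that no toxicity data exist for the four drugs together.
- The chemistry panel in Table 7 carries the liver tests, and the version log records that version 4.0 was partly meant to reduce the risk of hepatotoxicity.
- Section 8.1.1.1 already accepts the principle for imaging, where it warns that assessing the arms differently can bias the analysis. The laboratory maximum has no such safeguard.

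**Working it through.** The plan gives no figure of its own to reproduce here.

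**Step 1: count and align the draws.** Subtract the first checkpoint day (Day 10 with UV1, Day 1 in control). Safety follow-up is taken at 30 days after the last induction dose: 73 + 30 = 103 and 64 + 30 = 94.

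| Days from first nivolumab/ipilimumab dose | UV1 arm | Control arm |
|---|---|---|
| 0 | Day 10 | none after baseline |
| 16 | Day 26 | none |
| 21 | Day 31 | Day 22 |
| 42 | Day 52 | Day 43 |
| 63 | Day 73 | Day 64 |
| about 93 | about Day 103 | about Day 94 |

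That is six draws against four. If the screening sample were baseline and Day 1 counted, it would be seven against five, still two more with UV1. Four draws match exactly on checkpoint exposure. The surplus is Day 10 and Day 26.

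**Step 2: assumptions.** The documents give neither the per-draw risk *p* of a shift nor the within-patient correlation. I take *p* = 2%, 5% and 10%, the same in both arms (no UV1 effect), with full schedules completed. Day 10 comes before any checkpoint dose, so I give it *p*/5. That fraction is also an assumption.

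**Step 3: independent draws.**

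- UV1: 1 − (1 − *p*/5)(1 − *p*)^5. At *p* = 5%: 1 − 0.99 × 0.95^5 = 23.4%.
- Control: 1 − (1 − *p*)^4. At *p* = 5%: 1 − 0.95^4 = 18.5% (18.6% in the simulation below).

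**Step 4: correlated draws.** A latent normal model with equal correlation between all of a patient's draws, 400,000 simulated patients per scenario. UV1 against control:

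| *p* | Independent | Correlation 0.5 | Correlation 0.8 |
|---|---|---|---|
| 2% | 10.0% vs 7.8% | 7.6% vs 6.3% | 5.3% vs 4.7% |
| 5% | 23.4% vs 18.5% | 16.9% vs 14.4% | 11.7% vs 10.5% |
| 10% | 42.1% vs 34.4% | 29.4% vs 25.8% | 21.0% vs 19.3% |

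If correlation instead decays with time between draws (scale 10 or 21 days), the 5% row gives 21.9% vs 18.1% and 19.6% vs 16.9%. The UV1 arm is higher in every scenario.

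**Step 5: one trial.** With 154 randomized 1:1 there are about 77 per arm. If the true percentages were 21.5% and 18.5%, UV1 would show the higher observed percentage in about 64% of trials, control in about 28%, with ties in the rest.

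**Step 6: after the fix.** On the four matched draws both arms have the same expectation: 18.5% each if independent and 14.4% each at correlation 0.5, for *p* = 5%.

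**The case against.** **The tables are descriptive and there are other views of the data.** This stands in part. No test is attached, and section 2.7 presents the trial as hypothesis-generating. A reader might infer that a sampling artefact could not be told from real toxicity. The documents do not support that: Days 31, 52 and 73 can be set against Days 22, 43 and 64 in the per-visit summaries, Grade 3 or higher results are listed, and potential drug-induced liver injury is reported as a serious event in both arms (section 8.3.1.4). But the per-visit summaries are not by grade, so they do not replace a fair worst-grade comparison.

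**Six against four overstates the imbalance.** This stands. Treating all six draws as independent and equally risky gives 1 − 0.95^6 = 26.5% against 18.5%, a gap of 8 points. Day 10 precedes checkpoint exposure and Day 26 is close to Day 31, so the position is nearer five draws against four.

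**Worst grade over all draws is the cautious choice.** This also stands as a reason to keep that table. Day 10 is the only post-baseline draw after UV1 alone, and acute liver toxicity may appear in unscheduled samples.

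**Adverse events.** A reader might infer the same tilt in the non-serious event tables, because the rule is "All non-serious AEs should be reported from the first dose of induction therapy until 30 days after the last dose of induction therapy", which runs to about Day 103 with UV1 and Day 94 in control. The documents do not support that for checkpoint-driven events: from the first checkpoint dose the windows are 103 − 10 = 93 and 94 − 1 = 93 days. The nine extra days are on UV1 alone. Nor do the 9 against 5 inquiry visits show that events are missed in control, since patients are asked about the period since their last visit. Cutting both arms at Day 94 from first dose would leave 84 days of checkpoint follow-up with UV1 against 93. At a constant hazard giving 30% by 93 days, that is 1 − 0.7^(84/93) = 27.5% against 30%, a false deficit. Patient-time rates counted from Day 1 would also dilute UV1, by adding nine low-risk days to its denominator.

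**Conclusion.** The point holds for the worst-value laboratory shift table only. The six-against-four count follows directly from Tables 5 and 6, and so does the direction: with no UV1 effect the table is tilted against UV1 in expectation. It is not certain for any single parameter in a trial of this size.

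The likely size is modest: about 1 to 5 percentage points at an assumed 5% per draw (1.2 points at correlation 0.8, 2.5 at 0.5, 4.9 if independent). It rests on the assumed per-draw risk, the assumed correlation and the one-fifth weight for Day 10. Unscheduled tests, repeat liver panels and the undefined on-study period could move it either way. Section 9.4.1 leaves detail to a SAP, and the document reviewed contains no SAP text that settles the matter.

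**What to change.** In section 9.4.3 and the SAP:

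1. Define the on-study period for laboratory shift tables and say how unscheduled results are handled.
2. Base the between-arm worst-grade shift comparison on the scheduled draws matched on checkpoint exposure: before cycles 2, 3 and 4 (Days 31, 52 and 73 with UV1; Days 22, 43 and 64 in control) and at safety follow-up.
3. Keep the all-draws worst-grade table alongside it, including Day 10, Day 26 and unscheduled values, with a note that the number of draws differs by arm.

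The adverse event reporting window needs no change on this account.

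The cost is one extra table and a few lines of SAP text, with no new data. The matched table leaves out the Day 10, Day 26 and unscheduled values, so it must not stand alone: a UV1-specific or acute signal could appear only in the all-draws table.
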